Depending on which arm they are randomized to, participants will have their laceration closed by either DermabondTM, Steri-StripsTM, or absorbable sutures per the treatment arm protocols (Protocols, see Appendix IV). Unfortunately, given the nature of the study, neither the patient, parent nor health care provider will be blinded to the method of closure. Additional topical or injected anesthetics or the use of sedation will be left up to the patient/parent and provider's discretion. After the procedure, both patient (if older than 3 years old) and parent/guardian will be asked to fill out a short questionnaire (Questionnaires, see Appendix VI). The parent/guardian will be asked to rate the appearance of 3 images of random scars. All parents/guardians in the study will rate the same 3 scars to establish a baseline for each parent. The health care provider will also be asked to fill out a short questionnaire (Questionnaires, see Appendix VI). Upon discharge, the participant and their parent/guardian will be provided with verbal and written return precautions by the study staff (Care Instructions, see Appendix V).

Parents/guardians will be called 3 months after their initial visit for a brief over-the-phone interview (Questionnaires, see Appendix VI). At this time, they will be prompted to take a picture of the scar and send it to the Investigator by e-mail. A Vanderbilt email address has been set-up and is secure per Vanderbilt criteria. As an alternative, they can come back to the VCH ED where study staff will ask them a couple of questions in person and take a picture of the scar.

Every effort will be made to de-identify the images of the scar (using image editing software to crop everything on the image but the scar with some surrounding skin). The images will then be collected and presented to two Plastic Surgeons who will be blinded to the method of closure. They will subsequently score the scar as seen in the images (Questionnaires, see Appendix VI). All data will be collected on paper and then transferred to REDCap®. Each piece of data will be transferred to REDCap® by two study staff independently and then examined for any differences which can be reconciled by examining the paper forms. This will prevent errors in transferring data from paper to electronic format.

Participants will be compensated with a \$15 check after completion of the 3 month questionnaire and sending of photo.

Randomization

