Randomization will be accomplished using randomizer.org software to generate a set of 90 numbers from 1 to 3 for 90 enrolled participants. Each digit from 1 to 3 will correspond to a study arm.

Data Acquisition

Study data will be acquired through the means of the aforementioned questionnaires (Questionnaires, see Appendix VI), phone interviews, and by simple chart review. The secondary outcome of "cost of visit" will be acquired through Medical Records.

Institution/Hospital: Vanderbilt Children's Hospital

VIII. Predictor Variables

Predictor variables are the 3 treatment allocation arms: Dermabond[™], Steri-Strips[™], and absorbable sutures. Other independent variables to be collected include demographics of the patient (age, sex, race/ethnicity), specifics of the laceration (location, length and width, time between trauma and wound closure) and level of training of the provider who will be closing the wound. Demographics will be extracted from the patient Electronic Medical Record and from the parent Questionnaire (Questionnaires, see Appendix VI). Both the specifics of the laceration and the level of training of the provider will be extracted from the provider questionnaire at the time of the procedure (Questionnaires, see Appendix VI).

IX. Outcome Variables

a. Primary outcome variable

The primary outcome will be cosmesis of the resultant scar as measured on a 100 mm Visual Analogue Scale where a score of 0 corresponds to "worst scar" and a score of 100 corresponds to "best scar." This scale has been validated as a scoring method to evaluate cosmesis of a scar. 12, 16, 17, 23, 32 Due to its sensitivity and the fact that it provides parametric data, the scale allows for smaller, more practical sample sizes to show clinically-significant differences in populations. 12, 16, 17, 23, 32 The Visual Analogue Scale will be used by two Plastic Surgeons blinded to closure method to rate a patient's scar at 3 months. In addition, parents will be asked to rate the scar on a scale of 0 to 100 during their over-the-phone interview at 3 months. We will compare their rating of their child's scar to the average of their ratings of the 3 images of random scars at the initial visit.

b. Secondary outcome variables

i. Pain experienced by patient

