Patients and their parent/guardian(s) will be told very explicitly by the investigators that their participation in this research investigation is entirely voluntary and that they may withdraw at any time. We will further emphasize verbally and in the informed consent document that a decision on the part of the patient or parent/guardian(s) to not participate will in no way change, compromise or jeopardize the patient's care. Indeed, we anticipate that a number of eligible patients will not be enrolled on this basis.

XIV. Data Management

Participants' information (Subject Enrollment Form, see Appendix II, Questionnaires, see Appendix VI, pictures) will be kept in a separate file for each subject. Data will be transferred to the REDCap® server. This data will then be sent for statistical analysis.

XV. Statistical Considerations

We are planning a study of a continuous response variable from independent control and experimental subjects with 1 control per experimental subject. In previous studies, the response within each subject group was normally distributed with a standard deviation of 15 mm on a 100 mm Visual Analogue Scale and the minimal clinically important difference between two scars was 15 mm on a 100 mm Visual Analogue Scale. We performed multiple sample size power calculations using STATA® 14.1 (College Station, Texas). Using one-way ANOVA, with a power of 90% and an alpha of 0.05, we would need between 5 and 21 subjects per group to detect a clinically significant difference of 5 to 15 mm between groups depending on the standard deviation in each group (in anticipation of the fact that we may have a larger standard deviation). In order to assure an effective sample size after accounting for dropouts and missing data, we propose to recruit 30 experimental subject per treatment arm and 30 control subjects, for a total of 90 subjects.

XVI. Privacy and Confidentiality Issues

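### As Section VII reads, the parents' reference-scar ratings are taken after the unblinded closure, so the parent cosmesis comparison is referenced to a post-treatment value

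*Combined protocol and SAP*

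**What the plan says.** Section VII, Study Design, reads as a chronological account: enrollment, LET and wash-out, closure by the allocated method, questionnaires, discharge. On blinding it states that "neither the patient, parent nor health care provider will be blinded to the method of closure". It continues: "After the procedure, both patient (if older than 3 years old) and parent/guardian will be asked to fill out a short questionnaire". The next sentence is "The parent/guardian will be asked to rate the appearance of 3 images of random scars", followed by the purpose: "All parents/guardians in the study will rate the same 3 scars to establish a baseline for each parent". The provider questionnaire and the discharge instructions come after that.

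Section IX.a, under the primary outcome, first describes the ratings by two blinded Plastic Surgeons. It then adds that "parents will be asked to rate the scar on a scale of 0 to 100 during their over-the-phone interview at 3 months", and that the investigators will "compare their rating of their child's scar to the average of their ratings of the 3 images of random scars at the initial visit".

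No section places the reference rating before allocation or closure. None names the estimator for the parent comparison or says how an arm difference in the reference ratings would be checked or handled.

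**The concern.** The reference ratings are meant to remove differences between parents in how they use the 0 to 100 scale. That is safe when the reference cannot depend on the arm. Here the parent has apparently just seen the child's wound closed by a known method. The plan itself expects the arms to differ in pain, sedation and length of stay (Sections I and II), so the parent's experience shortly before rating the images may differ by arm.

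If that experience changes how parents score the images, the calibration adds a difference between arms instead of only removing differences between parents. The error can go either way. It can create an apparent difference between closure methods, or hide a real one. The second matters because the hypothesis in Section I is one of clinically equivalent cosmesis.

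**Working it through.** **Inputs from the documents.** Section XV says that "the response within each subject group was normally distributed with a standard deviation of 15 mm on a 100 mm Visual Analogue Scale". It also gives a minimal clinically important difference of 15 mm, alpha 0.05, power 90%, one-way ANOVA and 30 subjects per arm.

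**The plan's own figure.** Section XV gives no figure for the parent comparison, and none is disputed here. Its inputs do reproduce the upper end of its stated range of 5 to 21 per group: one-way ANOVA with three groups, means (0, 0, 15) and SD 15 needs 21 per group (power 91.5% at 21).

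**Inputs that must be assumed.** These are the arm shift *b* in the reference mean, the correlation ρ between the reference mean and the 3-month rating, and SD 15 mm for each of the two. Section XV's SD describes scar ratings in general, not the mean of three images or a difference from it. The calculation also assumes no true arm effect on the 3-month rating, a comparison of two arms at two-sided 5%, and full retention.

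**Model.** Let R be the parent's reference mean and Y the 3-month rating. Suppose one arm shifts R by *b*, and a fraction *p* of the shift persists in Y.

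- Difference score D = Y − R: bias in the arm contrast = (*p* − 1)*b*. With *p* = 0 this is −*b*.
- ANCOVA of Y on R: bias = (*p* − slope)*b*. With equal SDs the slope is ρ, so with *p* = 0 the bias is −ρ*b*.

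**Difference score, b = 5 mm, ρ = 0.5, p = 0, 30 per arm.**

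- SD of D = √(15² + 15² − 2 × 0.5 × 15 × 15) = 15 mm
- Standard error = 15 × √(2/30) = 3.87 mm
- Standardised bias = 5 / 3.87 = 1.29
- False-positive rate = 1 − Φ(1.96 − 1.29) + Φ(−1.96 − 1.29) ≈ 25%

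**ANCOVA, same inputs.**

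- Bias = 0.5 × 5 = 2.5 mm in size
- Residual SD = 15 × √(1 − 0.5²) = 12.99 mm
- Standard error = 12.99 × √(2/30) = 3.35 mm
- Standardised bias = 2.5 / 3.35 = 0.75
- False-positive rate ≈ 12%

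A simulation of 5,000 trials at these values gave mean biases of −4.95 mm (difference) and −2.52 mm (ANCOVA), in agreement with the formulas.

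**Range, 30 per arm, p = 0 (false-positive rate: difference score / ANCOVA).**

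| Shift *b* | ρ = 0 | ρ = 0.3 | ρ = 0.5 | ρ = 0.7 |
|---|---|---|---|---|
| 2 mm | 6.5% / 5.0% | 7.2% / 5.3% | 8.1% / 6.0% | 10.2% / 8.0% |
| 5 mm | 15.0% / 5.0% | 19.4% / 6.9% | 25.2% / 11.6% | 38.5% / 24.4% |
| 10 mm | 44.7% / 5.0% | 58.8% / 12.8% | 73.3% / 32.0% | 91.5% / 71.6% |

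**Sensitivity at b = 5 mm, ρ = 0.5.**

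- Three-arm omnibus ANOVA on the difference score, one arm shifted: 24.0%.
- 21 per arm instead of 30: 19.1% (difference score), 9.6% (ANCOVA).
- Half of the shift persisting (*p* = 0.5), difference score: net bias 2.5 mm, 2.5 / 3.87 = 0.65, about 10%.
- Full persistence (*p* = 1), difference score: bias 0, so 5%. Under ANCOVA the bias is then (1 − 0.5) × 5 = 2.5 mm in the opposite direction.

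**Could the shift be seen afterwards?** Comparing R between two arms of 30 with SD 15 is the same calculation, 5 / 3.87. Power to detect a 5 mm shift is therefore about 25%, and the check would miss it about three times in four.

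**The case against.** The case on the other side is substantial, and several parts of it stand.

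- **Timing.** The sentence on the three images has no time marker of its own, Section IX.a says only that the ratings belong to the initial visit, and the Appendix VI questionnaires are not in the text reviewed. This stands. Rating after closure is the natural reading, but the sponsor should confirm it.
- **Estimator.** Section IX.a says only that the ratings will be compared. Full carry-over needs a difference score. Under ANCOVA at correlation 0.5 it is half.
- **Persistence.** If the closure experience changes a parent's use of the scale and the change lasts 3 months, a difference score cancels it, and an earlier reference rating would not. The documents favour neither case. A lasting change of this kind belongs to the bias from the unblinded 3-month rating.
- **Evidence.** Nothing in the documents shows that seeing a repair alters ratings of unrelated scars. Every shift size above is assumed.

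Three stronger readings are tempting but not supported. A reader might infer that a shift could never be told apart from a true scar difference. However, all parents rate the same three images in randomized arms, so the reference means can be compared by arm, though with low power. The unreferenced parent rating and the blinded surgeons' ratings are also available. A reader might infer that the whole primary outcome is compromised. The surgeons' scores do not use the reference, and the cut-off for poor cosmetic outcome in Section IX.b applies to the rating itself. A reader might also infer that the reference and 3-month ratings may freely come from different guardians. The wording of Sections VII and IX.a already describes a comparison within one parent; only an explicit rule is absent, and the forms that might record the rater are not in the text reviewed.

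**Conclusion.** The point holds as a conditional one. As Section VII reads, the reference is a post-treatment value from an unblinded rater, so it lacks the protection that a pre-allocation baseline would have. If the closure experience shifts it by arm, the parent comparison is biased by the full shift for a difference score with no persistence, and by slope times shift under ANCOVA.

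A 5 mm shift would be one third of the plan's 15 mm important difference. The false-positive rates of about 25% and 12% rest on that assumed shift, SD 15 mm, correlation 0.5 and 30 per arm. They illustrate sensitivity and do not predict what this trial will show.

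The issue is confined to the parent comparison and does not reach the surgeons' ratings. Correcting it would not remove the bias from the parent's own unblinded rating at 3 months. It is worth correcting because the remedy is simple, not because harm has been shown.

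**What to change.** In Section VII, state that the parent or guardian rates the three images after consent and before the allocation is disclosed. The reference then cannot depend on the arm, by design.

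The cost is small: the same images, the same visit, no change in sample size, and one sentence in the protocol. The one practical burden is that the allocation must stay concealed until the rating is finished. The Randomization text does not say when the allocation is revealed, so this may need a small change in workflow.

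If ratings have already been collected after closure, report the reference ratings by arm and show the unreferenced parent rating as a sensitivity analysis. A non-significant arm comparison of the reference ratings should not be taken as proof that there was no shift, given the low power shown above.

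### The allocation list of 90 digits does not guarantee the planned 30 per arm (small cost), and the one method named has no term for laceration location

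*Combined protocol and SAP*

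**What the plan says.** Section VII, Randomization, gives the whole scheme in two sentences: "Randomization will be accomplished using randomizer.org software to generate a set of 90 numbers from 1 to 3 for 90 enrolled participants", and "Each digit from 1 to 3 will correspond to a study arm". It mentions no blocks, no strata and no requirement that each digit appear 30 times.

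Section XV (Statistical Considerations) describes the design as having "independent control and experimental subjects with 1 control per experimental subject" and ends with "we propose to recruit 30 experimental subject per treatment arm and 30 control subjects, for a total of 90 subjects". The only statistical method named is in the same paragraph: "Using one-way ANOVA, with a power of 90% and an alpha of 0.05, we would need between 5 and 21 subjects per group". The planning SD and the minimal clinically important difference are both 15 mm.

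Section VIII (Predictor Variables) lists, among the other independent variables to be collected, "specifics of the laceration (location, length and width, time between trauma and wound closure". No section says that location will be stratified on or adjusted for. Section V excludes some sites and leaves the rest eligible.

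On blinding, section VII states that "neither the patient, parent nor health care provider will be blinded to the method of closure". Only the plastic surgeons who rate the scars are blinded.

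**The concern.** The randomization and sample-size sections should describe the same trial. Section XV treats 30 per arm as fixed, but the procedure in section VII would deliver that only if the digits were forced to equal counts, which it does not say. Without that constraint the arm sizes are random. The suture arm enters both adhesive-versus-suture comparisons, so its size affects both intervals, and it is as likely to come out above 30 as below.

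The second part concerns precision. A one-way ANOVA has arm as its only factor. If scar scores differ by body site, that variation stays in the residual, although the variable that would remove it is already on the provider questionnaire.

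**Working it through.** **1. Reproducing the plan's figure.** Inputs from section XV: one-way ANOVA, three groups, alpha 0.05, power 90%, SD 15 mm, difference 15 mm. The section does not state the pattern of means. I take one arm differing, (15, 0, 0), with grand mean 5. The noncentrality is

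λ = n × Σ(μᵢ − μ̄)² / SD² = n × (100 + 25 + 25) / 225 = 2n/3,

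referred to F with 2 and 3n − 3 degrees of freedom.

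- n = 20: power 89.97%
- n = 21: power 91.5%
- n = 29: power 97.9%
- n = 30: power 98.2%

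The smallest n reaching 90% is 21, the upper end of the stated range, so this is a fair model for the comparison below.

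**2. Arm sizes if the digits are independent.** The counts are multinomial (90; 1/3, 1/3, 1/3).

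- SD of one arm's size: √(90 × 1/3 × 2/3) = 4.5; central 95% range 21 to 39
- Probability of exactly 30/30/30: 0.9%
- Mean smallest arm: 25.4
- Probability that largest minus smallest is 10 or more: 44%

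**3. Cost in power.** Averaged over all possible allocations, power is 97.9% against 98.2% with 30 per arm. That equals the power of 29 equal subjects per arm, so the loss is worth about one subject per arm. With evenly spaced means (0, 7.5, 15) the figures are 93.1% against 93.6%.

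Section XV gives no loss rate; going from 21 to 30 leaves room for 30% loss (21/30 = 0.70). With 63 analysed (0.70 × 90) and means (15, 0, 0), power is 91.5% with equal arms and 90.7% on average without the constraint. The 5th percentile over allocations is 84.8%.

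**4. Cost in interval width.** The 95% half-width for a pairwise difference, with pooled SD, is

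t(0.975, 87) × 15 × √(1/n₁ + 1/n₂).

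At 30 and 30 this is 1.988 × 15 × √(2/30) = 7.70 mm. Averaged over the multinomial allocations it is 7.78 mm.

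**5. Predictability.** Suppose someone knows all earlier allocations and guesses the least-used arm each time. By simulation the guess is right 33% of the time with independent digits, 41% with a single shuffled 30/30/30 list, and 58% with ten blocks of 3 and ten of 6 in random order.

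**6. Location.** The documents give neither the share of facial lacerations nor the effect of site on the score, so both are assumed. Let p be the facial share, d the difference between face and elsewhere, and 15 mm the total SD. The residual SD after adjustment is √(225 − p(1 − p)d²). The half-width is t(0.975, 86) × residual SD × √(2/30); one degree of freedom is spent.

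| p | d (mm) | Residual SD (mm) | Half-width (mm) |
|---|---|---|---|
| 0.3 or 0.7 | 5 | 14.8 | 7.6 |
| 0.3 or 0.7 | 10 | 14.3 | 7.3 |
| 0.3 or 0.7 | 15 | 13.3 | 6.8 |
| 0.5 | 5 | 14.8 | 7.6 |
| 0.5 | 10 | 14.1 | 7.3 |
| 0.5 | 15 | 13.0 | 6.7 |

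The unadjusted value is 7.7 mm.

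**The case against.** Simple randomization is valid and unbiased, and its cost here is about 0.3 power points. Section XV states the intended arm sizes, so the two sections can be read as leaving a detail unsaid rather than contradicting each other. Every imbalance figure above is conditional on independent digits, which the text does not settle. All of this stands, and it limits the point to a clarification.

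The hypothesis is also one of clinical equivalence, for which omnibus ANOVA power is an imperfect yardstick. That too is fair; the half-width in step 4 answers it and shows an equally small cost.

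On location, the ANOVA appears only in the sample-size paragraph and is never declared the primary analysis. A reader might infer that the plan has decided to leave location out. The documents do not show that: the primary model is simply not specified. Nor do they show that location predicts the score better than age, wound length and width, time to closure or provider training, all of which are also collected. At the low end of the assumed range the gain is only 0.1 mm.

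Small permuted blocks are a tempting remedy, but with closure open-label they raise correct guessing to 58%, a poor exchange for so small a gain. They should not be the lead option.

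**Conclusion.** The point holds, at minor severity. As written, section VII does not guarantee the 1:1:1 allocation that section XV assumes. If the digits are independent, the average cost at full enrolment is 98.2% to 97.9% in power and 7.70 to 7.78 mm in half-width, at SD 15 mm and a 15 mm difference.

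A reader might infer that the comparison is biased or the trial underpowered as a result. Neither follows. Unequal arm sizes arising by chance do not bias the comparison, and at full enrolment average power stays well above the stated 90%. With 30% loss, most of the fall in power comes from the loss itself. Chance imbalance in location is likewise not bias, because the unadjusted standard error already allows for it.

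Adding location needs no new data, but its benefit is conditional: little if location is weakly prognostic, and up to about 1 mm of half-width (7.7 to 6.7) at the top of the assumed range. Confidence is high in the missing text and the arithmetic, and lower in the size of the gain from location.

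**What to change.** Before first enrolment, shuffle 30 of each digit into one list, keep it concealed from the staff who enrol, and say so in section VII. This gives exactly 30/30/30 if all 90 are enrolled. It costs one regenerated list and a modest rise in predictability (about 41% against 33% correct guesses), which is why concealment belongs in the same sentence. If enrolment stopped early the arms could still differ: at 60 children the mean gap between largest and smallest is 4.4, against 7.6 with independent digits.

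If the simple list is kept, state in section XV that 30 per arm is an expected size and that arm sizes will vary.

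Separately, state in section XV that the primary model contains arm and laceration location (face versus elsewhere). This costs one sentence and one degree of freedom. Stratifying the list by location is optional.

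### The plan implies a between-arm comparison of scar scores but states no analysis model and gives age and wound features no use; a prespecified ANCOVA is a cheap improvement whose gain is conditional

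*Combined protocol and SAP*

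**What the plan says.** Section II sets out to relate closure method to scar cosmesis, section VIII makes the three arms the predictor variables, and section XV uses one-way ANOVA to size the trial. No section names the model or the contrasts for the final analysis.

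Section IX.a defines the primary outcome as cosmesis on a 100 mm scale at 3 months. The scale "will be used by two Plastic Surgeons blinded to closure method", and no rule is given for combining the two scores. The same paragraph adds a second rating: "In addition, parents will be asked to rate the scar on a scale of 0 to 100". The comparison stated for it is of the parent's rating of the child's "scar to the average of their ratings of the 3 images of random scars at the initial visit".

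Section VII says that all parents "will rate the same 3 scars to establish a baseline for each parent", and that "neither the patient, parent nor health care provider will be blinded to the method of closure".

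Section VIII lists further independent variables to be collected: demographics including age, the level of training of the provider, and "specifics of the laceration (location, length and width, time between trauma and wound closure". The wound details and training level "will be extracted from the provider questionnaire at the time of the procedure". None of these variables is given a role in adjustment, stratification or subgroup analysis.

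**The concern.** Section I hypothesises that each alternative is clinically equivalent to sutures. For that question the interval for each arm versus sutures matters more than the omnibus F test. Variables known at enrolment that predict the scar score could narrow the interval at no cost in patients, but only if their use is fixed in advance. With the score and the model unstated, both could be chosen after the data are seen.

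The parent comparison raises a separate issue. Comparing a child's scar with three unrelated scars, within one parent, says how that parent ranks the scar. It does not say whether closure methods differ. The image ratings are useful as a measure of how severely each parent scores, and that use needs them as a covariate in a between-arm model.

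**Working it through.** **Inputs.** From section XV: SD 15 mm, minimal clinically important difference 15 mm, alpha 0.05, power 90%, up to 21 per group needed, 30 per arm recruited. Assumed: equal arms; R2 (the share of within-arm variance explained by the covariates) of 0 to 0.30, since the documents give none; 3 covariate degrees of freedom (age 1, face/other 1, length 1).

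**1. The plan's own figure.** With means (0, 0, 15) and SD 15, the noncentrality is n × Σ(μᵢ − μ̄)²/σ² = n × (25 + 25 + 100)/225.
- n = 20: power 89.97%.
- n = 21: noncentrality 14.0, power 91.5%. The plan's upper figure of 21 is reproduced.
- n = 30: noncentrality 20.0, power 98.2%.

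**2. Unadjusted half-width, one arm versus sutures.** t(87) × SD × √(2/n) = 1.9876 × 15 × √(2/30) = 7.70 mm. With 21 per arm it is 9.26 mm.

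**3. Adjusted half-width.** t × SD × √[(1 − R2) × (2/n) × inflation]. The inflation for chance imbalance in 3 covariates is 1 + 3/(3n − 7): 1.036 at n = 30 and 1.054 at n = 21. The error degrees of freedom fall from 87 to 84 at n = 30, where t = 1.9886.

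| SD 15, 30 per arm | Unadjusted | R2 0 | 0.05 | 0.10 | 0.20 | 0.30 |
|---|---|---|---|---|---|---|
| 95% half-width (mm) | 7.70 | 7.84 | 7.64 | 7.44 | 7.01 | 6.56 |
| Power, means (0, 0, 10) | 75.0% | 73.3% | 75.6% | 78.0% | 82.9% | 87.8% |
| Power, means (0, 0, 15) | 98.2% | 97.8% | 98.3% | 98.8% | 99.4% | 99.8% |

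A simulation of 8,000 trials per case (two continuous covariates and one binary) gave mean adjusted half-widths of 7.81, 7.63, 7.42, 6.99 and 6.53 mm, against about 7.68 mm unadjusted.

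**4. Break-even R2.** Setting the two half-widths equal at n = 30: R2 = 1 − 1/[1.0361 × (1.9886/1.9876)²] = 3.6%. The threshold rises with more covariates or fewer patients.

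| Covariate df | 30 per arm | 21 per arm |
|---|---|---|
| 3 | 3.6% | 5.3% |
| 5 | 6.0% | 8.8% |
| 8 | 9.6% | 14.1% |

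**5. If the SD is larger.** Section XV allows for this. Take SD 20 (assumed), 30 per arm, no true difference, and the plan's 15 mm as an assumed margin. The probability that the 95% interval lies within ±15 mm goes from 63.9% unadjusted to 61.1% (R2 = 0), 68.9% (0.10) and 76.7% (0.20).

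**The case against.** The strongest objection is that a reader might infer that the plan has no between-arm comparison at all, or rests its conclusion on the within-parent one. The documents do not support that. The aim in section II, the predictor variables in section VIII and the ANOVA in section XV together imply a comparison by arm, and one-way ANOVA would be a valid test of a difference. What is missing is a statement of it as the analysis. The rule for combining the surgeons' scores is likewise missing detail, not an error.

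The image ratings may have been meant as rater calibration ahead of an arm comparison. That is plausible, but the text stops short of the arm comparison. A reader might also infer that these ratings are definitely taken after closure, and so could be influenced by it. Section VII places "The parent/guardian will be asked to rate the appearance of 3 images of random scars" after the sentences on the post-procedure questionnaires but gives it no time of its own. Section IX.a says only that it happens at the initial visit. The timing is therefore an inference from sentence order.

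The benefit is also small at the plan's own values: 0.26 mm of half-width and 0.6 points of power for 15 mm at R2 = 0.10. Single linear wounds under 5 cm may leave the covariates little to explain. In step 5, a 90% interval, which corresponds to two one-sided 5% tests, gives 78.4% unadjusted and 81.9% at R2 = 0.10, a gain of 3.5 points instead of 5.0. SD 15 may describe a single rating, in which case averaging two surgeons would by itself lower the SD. All of this stands, and it limits the point to an optional gain in precision.

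**Conclusion.** The point holds as a low-cost improvement and not as a flaw that invalidates the trial. A between-arm analysis is implied but no model is stated, the collected covariates have no use, and the parent comparison as written does not contrast arms.

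Whether adjustment helps depends on an R2 that nobody has documented. The 3.6% threshold applies only to exactly 3 covariate degrees of freedom with all 90 patients analysed. If the covariates explain nothing, the interval is 2% wider (7.84/7.70 = 1.02) and the power loss is under 2 points: 1.7 points for 10 mm with 30 per arm, and 1.6 points (91.5% to 89.9%) for 15 mm with 21 per arm. Since power for 15 mm is already 98.2% with 30 per arm, the benefit is mainly precision.

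A reader might also infer that ANCOVA would settle the equivalence hypothesis. It would not: section XV gives a minimal important difference, but nothing in the documents labels it as an equivalence margin.

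**What to change.** - **Primary analysis.** State the primary score as the mean of the two blinded surgeons' 3-month ratings. Analyse it by ANCOVA with arm, age, location (face/other) and length. Report each alternative versus sutures with its confidence interval, and show the unadjusted contrast as a sensitivity analysis.
- **Parent rating.** Make it a secondary outcome, contrasted between arms with the three-image mean as a covariate. This lets the data set the weight of the image mean, whereas subtracting it would fix that weight at one.
- **Timing.** Where possible, take the image ratings and wound measurements before allocation is revealed. Otherwise, also report the parent contrast without the image covariate.
- **Equivalence.** State the margin separately, because the model does not supply one.

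The cost is a few sentences of analysis text, three error degrees of freedom and a small change in when two existing items are collected. No new variables or patients are needed. Keep the covariate list to these three, because each added term raises the break-even R2.
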